5. STUDY INTERVENTIONS

5.1 Interventions

Overview: In this three-arm multisite, randomized controlled pilot and feasibility trial, mindfulness-based intervention (MBI), cognitive-behavioral therapy (CBT), and health education (HealthEd) group programs are matched for time, attention, and facilitator training. All

interventions will be delivered for six weekly 1-hour group-based sessions. Group sessions will either take place via secure videoconferencing or in a conference room at each respective site. All interventions will be delivered by a clinical or counseling psychologist. Programs will be co-facilitated by a graduate student in clinical or counseling psychology, social work, prevention science, or related field, or a research associate with a master's degree in clinical or counseling psychology, social work, prevention science, or related field. To minimize facilitator effects, the lead psychologist facilitators at each site will facilitate all three programs. All facilitators and co-facilitators will receive training and weekly supervision as described below. Interventionists cannot be blinded to intervention assignment due to the nature of the intervention.

Intervention Training: All three interventions are manualized. Utilization of manuals for each of the three conditions supports fidelity, which will be closely monitored. Prior to delivery of the interventions as part of the multisite, pilot clinical trial, lead psychologist facilitators and co-facilitators will participate in MBI, CBT, and HealthEd training. The training will be 5-days (~3 days for MBI, ~1 day for CBT, ~1 day for HealthEd). We prefer to conduct the training in-person, but if circumstances (e.g., due to COVID-19) are more conducive to remote training, we will deliver some or all portions of the training remotely via videoconferencing. All trainings will video-recorded for future reference/training by the study team.

Training will include presentations of theoretical/empirical background, review of manuals, modeling of session elements, and role-play in mock-groups. [name] (Co-I), a psychologist completing BREATHE master training certification with [name] (Consultant; BREATHE developer), will lead training in BREATHE, the MBI program. [name] has expertise delivering BREATHE with high fidelity/competence to at-risk teenagers. [name] (Co-I), a psychologist trained in the Blues Program by [name] (Consultant) and his team of Blues Program developers ([name], [name]) and in HealthEd by [name] (PI), will facilitate training in the CBT Blues Program and the didactic control program, HealthEd. [name] has demonstrated high fidelity/competence in CBT and HealthEd, as rated by the Blues Program development team and [name].

To assess training fidelity: a) MBI, CBT, and HealthEd training sessions will be video-recorded and rated by [name], [name], and [name], respectively, on training fidelity forms; b) Facilitators will complete post-training surveys assessing quantitative knowledge of MBI, CBT, and HealthEd, following the didactic portion of the training; and c) Facilitators' adherence and competence in conducting mock intervention sessions will be evaluated by experts (Drs. [name], [name]/[name]/[name], and [name]) on standardized ratings scales to establish training fidelity prior to delivery to participants. Facilitators also will provide qualitative feedback on any recommended modifications to training procedures that they perceive would improve the training process, for use in a future NIH/NCCIH UG3/UH3 grant application/multisite efficacy trial. For descriptive purposes, facilitators will complete surveys of quantitative intervention knowledge prior to the didactic training, as well as feedback following the mock session training portion.

Intervention delivery: Supervision and fidelity monitoring: Sessions will be audio-recorded and reviewed weekly by [name] (MBI) and [name] (CBT, HealthEd) for intervention fidelity/adherence and facilitator competence. Feedback will be provided in weekly supervision. Facilitators with drift or deficiencies will be re-trained via "booster sessions" as needed. These protocols have been successful, as evidenced by strong ratings of adherence, competence, and absence of cross-contamination.^{56,57,128,130} Blinded experts will review audio-recorded sessions and complete standardized/structured rating scales of fidelity/competence in administration of MBI, CBT, and HealthEd. Non-participant/non-experts (e.g., trained undergraduate research assistants) also will complete ratings of intervention adherence.

Intervention acceptability: Attendance and home practice will be tracked at all sessions. Adolescents will report homework completion to facilitators, and also will record completion of home practices on journal logs for MBI and CBT. Adolescents will complete a weekly acceptability form.¹³¹

Group cohesion, therapeutic alliance, and expectancies: We will measure group cohesion and therapeutic alliance using two independent raters' review of audio-recorded sessions using the Therapy Process Observational Coding System, which shows good psychometric properties.¹³² Raters will be blind to group assignment.

Adolescents will complete the reliable and valid 12-item Therapeutic Alliance Scale for Adolescents (TASA)¹³³ to assess their perceptions of their emotional bond and task collaboration both early (session 1) and at the end (session 6) of the interventions.¹³³⁻¹³⁵ Finally, as a quantitative index of outcome expectancy, we will ask adolescents to report at the end of session 1, their perspective of the likelihood that their stress, mood, and risk for T2D can be improved.¹³⁶

5.2 Prohibited Interventions

Adolescents will not be enrolled if they are currently engaged in regular psychotherapy, medication treatment that could affect mood, weight, insulin sensitivity, or cortisol secretion, or a structured weight loss program.

5.3 Allowed Interventions

Adolescents who are receiving counseling at school or through a non-professional counselor (e.g., church or religious affiliation), or adolescents who are not receiving regular weekly or biweekly psychotherapy (e.g., once per month) will not be excluded. Adolescents who are taking medications that do not affect mood, weight, cortisol, or insulin sensitivity will be allowed to participate. Likewise, adolescent females who are stabilized on birth control (~3 months) will not be excluded.

5.4 Adherence Assessment

Adolescents' adherence to the intervention will be measured by their attendance of MBI/CBT/HealthEd sessions. The benchmark for intervention adherence will be 5 out of 6 group sessions. An intervention session progress note will include an attendance log to track group session attendance, as well as make-up sessions. All adolescents who miss a group session in any of the three intervention arms will be invited to complete a make-up session to review the key material prior to the next group. If interventions overlap with holidays, an alternative day of the week will be offered (e.g., Tuesday instead of a Monday) or two consecutive group sessions may need to occur 2 weeks apart instead of 1 week (e.g., to avoid winter holiday break when many families are unavailable). Brief homework (10 minutes/day) in MBI and CBT will be tracked by participants on intervention participant workbooks, and also reported to facilitators at the start of session 2-6. Intervention adherence is calculated at the end of each cohort; attendance of at least 5 of the 6 group sessions is incentivized (\$50). Total intervention adherence by arm, across sites, and homework completion will be described at the end of the study. Intervention adherence will be presented to the IMC and on the continuing review submitted to the IRB.

6. STUDY PROCEDURES

The overview of key study procedures for this multisite, pilot clinical trial is provided in **Table 7**.

6.1 Schedule of Evaluations

Table 7. Overview of key study procedures/assessments throughout the trial

Construct: Assessment	Screening/ Baseline Visit 1	Baseline At-Home Collection	Screening/ Baseline Visit 2	Randomization: MBI, CBT, or HealthEd 6-week Group				6-week Follow-up	6-week At-Home Collection	1-year Follow-up	1-year At-Home Collection
Informed consent/assent	X										
BMI indices: Height & weight	X		X					X		X	
Medical & family history	X							X		X	
Good general health: Physical & puberty exam	X*		X*							X	
Depression: CES-D survey (pre-screen)	X							X		X	
Psychopathology: Medical history & K-SADS interview	X							X		X	
Insulin sensitivity: OGTT			X					X		X	
Body composition: BodPod measurement			X					X		X	
Stress-related behavior											
Hedonic eating: Interview, survey, & laboratory test meal			X					X		X	
Physical activity: ActiGraph		X						X	X		X
Stress-related physiology											
Stress reactivity: Trier Social Stress Test			X							X	
Cortisol dysregulation: Saliva		X							X		X
BMI: body mass index indices derived from height and weight. CBT: cognitive-behavioral therapy; CES-D survey: Center for Epidemiologic Studies-Depression Scale, assessed at the phone pre-screen phase; HealthEd: health education; K-SADS: Schedule for Affective Disorders and Schizophrenia for School-Age Youth – Computerized Version semi-structured interview; MBI: mindfulness-based intervention; OGTT: oral glucose tolerance test; T2D: Type 2 diabetes. *Exam may be completed at either screening visit based upon medical provider availability.											

6.2 Description of Evaluations

6.2.1 Phone Screening Evaluation

We will conduct a phone screen to estimate eligibility. The phone screen will estimate the inclusion criteria of: age, height and weight to estimate BMI percentile, and family history of T2D; and the exclusion criteria of: major medical problem and exclusionary medication use. At this stage, we also will have adolescents complete a REDCap survey of the CES-D depression measure to determine the inclusion criterion for elevated depression symptoms (CES-D total score >20). Adolescents who cannot easily access REDCap may be screened by CES-D interview (i.e., asking the questions by phone). We have used the same approach in previous studies (e.g., COMIRB protocol #16-2571). Using this approach, approximately 74% of adolescents who meet eligibility criteria by phone screen also meet eligibility criteria when they proceed to the consent and screening/baseline assessment phase.

Adolescents who appear to be eligible following the phone screening phase will be scheduled for a series of two screening/baseline assessment appointments. The first screening/baseline assessment may take place either remotely via secure video software/phone or in-person. The second screening/baseline assessment will be conducted in-person in the laboratory. Laboratory assessments will be collected at one of the four sites: (i) the Pediatric Clinical and Translational Research Center (CTRC) at Children's Hospital Colorado, (ii) the Human Performance and Clinical Research Laboratory at Colorado State University, (iii) the Military Cardiovascular Research Outcomes Program at the Uniformed Services University, or (iv) the Children's Research Institute at Children's National Medical Center. Ambulatory measures of physical activity and cortisol will be assessed in between the first and second screening/baseline appointments.

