4. SELECTION AND ENROLLMENT OF PARTICIPANTS

4.1 Inclusion Criteria

Participants must meet all of the following inclusion criteria in order to participate in this study: a) 12-17 years of age; b) overweight or obesity, as determined by a BMI ≥ 85 th percentile for age and sex; c) elevated depression symptoms, as determined by a total score that exceeds 20 on the Center for Epidemiologic Studies-Depression Scale (CES-D); d) at least 1 first- or second-degree relative with T2D, prediabetes, or gestational diabetes; e) good general health, as determined by medical history and physical examination, and f) parent/guardian of qualifying participant. These criteria are outlined in **Table 5**.

Table 5. Inclusion criteria

Inclusion Criteria
a) Adolescent: Age 12-17 years
At-risk for T2D:
b) Overweight/obesity: BMI ≥ 85 percentile for age and sex
c) Family history of T2D: ≥ 1 relative with T2D, prediabetes, or gestational diabetes in first- or second- degree relative, referring to a biological parent, sibling, aunt, uncle, or grandparent
d) Elevated depression symptoms: Center for Epidemiological Studies – Depression Scale (CES-D) total score > 20
e) Good general health: Medical history/physical examination
f) Parent/guardian: Parent/guardian of qualifying participant

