Upon completion of all screening and baseline assessments, a research staff will notify the adolescent and their parent/guardian that they completed all screening and baseline assessments and are eligible. The ideal window is that screening/baseline assessments will occur within 12 weeks/3 months of the start of the intervention phase (first group session); we will allow for up to 6 months between screening/baseline and group initiation. In the event that more than 6 months transpires since the screening/baseline interval, all interested adolescents who appeared to be eligible or who had been determined to be eligible, will be invited to complete a re-screening, referring to a repeat of all screening/baseline assessments. Re-screening will only be offered if there is sufficient opportunity for the participant to take part in a subsequent intervention cohort (e.g., originally screened for cohort 1, but after >6 months, could be re-screened to be considered for participation in cohort 2). After all screening/baseline assessments are complete and prior to randomization, adolescents and parent/guardians will be asked to confirm their desire to continue to participate in the study. Adolescents and parents will each, independently report their preference for group condition (MBI, CBT, HealthEd, or no preference). Adolescents then will be randomly assigned to either a MBI, CBT, or HealthEd group using the RedCAP randomization module by the lead study coordinator. Date of randomization will be considered date of enrollment.

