Another purpose of secondary analyses is to supplement the mixed-methods analyses in Aim 3 used to refine study procedures and interventions in preparation for a future efficacy trial by understanding predictors associated with study outcomes, as well as mediators and moderators of intervention effects. This study is not designed as an efficacy study, and we will not necessarily have sufficient statistical power for the secondary analyses. However, results of these analyses may help inform changes to the interventions. We will examine predictors of participant attrition, attendance, and likability/credibility ratings. We will use multilevel mixed-effects models to examine change over time in measures of depression, insulin resistance, stress-related behavior, and stress physiology. These models will allow us to account for and estimate the correlation within study site and intervention cohort, as well as the correlation between repeated measures within a participant. ICC will be estimated using the method of Donner¹⁷⁹ for continuous variables and Ridout¹⁸⁰ for binary variables. The models will contain terms for group, time, and a group by time interaction. We will adjust for the baseline value of the outcome, and will also consider adjustment for baseline age, sex, race/ethnicity, particularly if these variables are not balanced across study groups. Models will be adjusted for baseline adiposity and change in adiposity to examine whether decreases in depressive symptoms improves insulin sensitivity independent of adiposity. If we find significant between-group differences in the insulin resistance, stress-related behavior, and stress physiology outcomes, we will test whether those effects are moderated by baseline depressive symptom severity (CES-D score) by including an interaction term in the model. We will also examine participant characteristics associated with these outcomes in order to better understand factors that moderate the response to intervention. Mediation analyses, using the product-of-coefficients method and bootstrapped standard errors, will be used to explore whether improvements in insulin sensitivity (if present) are mediated by changes in stress-related behaviors and stress physiology. Quantitative measures of group cohesion, therapeutic alliance, and perceived credibility/expectancy, summarized by intervention arm, will inform modifications to facilitator training, optimization of interventions, and study design in the larger trial. Finally, we will examine theoretical therapeutic mechanisms to explore the hypotheses that in MBI, mindfulness, monitoring/acceptance, and executive function will improve and in CBT, thoughts and pleasant activities will improve, compared to each other and to HealthEd.

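### The only CES-D described before treatment is the phone-screen score that selects adolescents, and the plan reuses it as the analysis baseline

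*Combined protocol and SAP*

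**What the plan says.** Section 6.2.1 (phone screening) states: "At this stage, we also will have adolescents complete a REDCap survey of the CES-D depression measure to determine the inclusion criterion". The threshold there and in Section 4.1 is a total above 20. The same section allows a second mode: "Adolescents who cannot easily access REDCap may be screened by CES-D interview".

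The Table 7 footnote agrees on timing: "CES-D survey: Center for Epidemiologic Studies-Depression Scale, assessed at the phone pre-screen phase". The row itself is labelled as pre-screen, but its only pre-treatment mark stands in the Screening/Baseline Visit 1 column.

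Sections 6.2.2 and 6.2.3 (the two screening visits) and the baseline measures in 6.2.4 list many surveys and interviews, but no CES-D. The next one is at the 6-week follow-up, where Section 6.2.6 counts it among baseline assessments being repeated.

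On timing, Section 6.2.4 gives 3 months as ideal and adds: "we will allow for up to 6 months between screening/baseline and group initiation". Beyond that, adolescents are invited to repeat the screening/baseline assessments.

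On analysis, Section 8.6.2 says of the longitudinal models: "We will adjust for the baseline value of the outcome". It also plans to test baseline CES-D as a moderator of the insulin resistance, stress-behavior and stress-physiology outcomes, if those show significant between-group differences.

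**The concern.** One score does two jobs. It selects adolescents because it is high, and it is then the starting point from which depression change is measured. A group chosen for high scores on one occasion is expected to score lower on average at the next, with no intervention at all. Months of waiting add room for natural remission.

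Section 7.2 anticipates improvement in all three arms, including HealthEd, and Section 2.2 cites percent symptom reduction as evidence from the sponsor's earlier pilot. Read the same way here, within-arm improvement could not be separated from regression to the mean. Cutting the distribution at 20 also narrows the spread of baseline scores, so the baseline explains less of the follow-up variance and gives a moderation test less to work with.

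The protocol already avoids this for BMI. Section 6.2.2 uses an early value to estimate eligibility and the second-visit measurement as baseline. Depression, one of two outcomes named for the efficacy signal in Section 8.6.2, has no such step.

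**Working it through.** The plan states no figure for this point, so there is none to reproduce. The documents give no CES-D mean, SD or retest correlation. The following are assumptions: screened-population mean m = 14, 16 or 18; SD s = 9, 10 or 11; screen-retest correlation r = 0.5, 0.6 or 0.7; bivariate normal scores. The cut-off of 20 is from Section 4.1.

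**Regression to the mean.** With c = (20 - m)/s and λ = φ(c)/P(Z > c), the selected mean is m + sλ and the expected fall without treatment is (1 - r)sλ.

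| m, s, r | λ | Selected mean | Expected fall |
|---|---|---|---|
| 18, 9, 0.7 (smallest) | 0.945 | 26.5 | 0.3 × 9 × 0.945 = 2.6 (10%) |
| 16, 10, 0.6 (middle) | 1.069 | 26.7 | 0.4 × 10 × 1.069 = 4.3 (16%) |
| 14, 11, 0.5 (largest) | 1.174 | 26.9 | 0.5 × 11 × 1.174 = 6.5 (24%) |

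Over the whole grid the selected mean is 25-28, and 29-52% would score 20 or below on retest.

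**Range restriction.** The variance left after selection, relative to the unselected variance, is v = 1 - λ(λ - c). For m = 16, s = 10: c = 0.4 and v = 1 - 1.069 × 0.669 = 0.285, so the SD is √0.285 = 0.53 of its unselected value.

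**Precision.** Illustrative correlations before selection: screen with pre-group 0.6, pre-group with follow-up 0.6, screen with follow-up 0.5. With k = 1 - v = 0.715, selection on the screen score gives:
- follow-up variance 1 - 0.25k = 0.821; pre-group variance 1 - 0.36k = 0.743
- screen with follow-up: 0.5 × 0.285/√(0.285 × 0.821) = 0.29; residual variance 0.91
- pre-group with follow-up: (0.6 - 0.30k)/√(0.743 × 0.821) = 0.49; residual variance 0.76

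The ratio 0.76/0.91 is about 0.83, or 17% less residual variance. Its square root is 0.91, or about 9% off the standard error.

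**Between-arm contrast.** 20,000 simulated two-arm baseline-adjusted comparisons were run with 34 per arm (40 less the 15% loss assumed in Section 8.2), baseline cut at the top third and r = 0.4, 0.6 and 0.8. A true effect of 0 was estimated as 0.00, with 4.8-4.9% rejections at the two-sided 5% level. A true effect of 0.30 SD was estimated as 0.30. The control arm nevertheless fell by 0.65, 0.44 and 0.22 SD for those three correlations.

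**The case against.** Much of the opposing case stands. A reader might infer that every depression analysis is compromised. The documents do not support that: baseline precedes randomization, so the fall is expected equally in all arms, and the planned signal is a one-sided 80% confidence interval for the treatment effect. No listed primary or secondary endpoint uses CES-D change. The moderator is conditional and concerns other outcomes. Section 8.6.2 itself warns that power may be insufficient for secondary analyses.

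A reader might also infer that the score can be older than 6 months. Section 6.2.4 allows up to 6 months and offers re-screening beyond that. What is missing is whether the clock starts at the phone screen, and whether re-screening repeats the CES-D; the gap between phone screen and Visit 1 has no stated limit.

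The Table 7 mark under Visit 1 is a contrary sign. It does not outweigh the row label, the footnote and the absence of any CES-D from the visit procedures. If a Visit 1 CES-D is intended, the text needs to say so. The mood form completed at each session gives some symptom information when groups begin, but it is not described as a CES-D and its scoring is not given. The 74% carry-through in Section 6.2.1 covers all eligibility criteria and is not a CES-D retest.

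Finally, Section 3.6 expected enrollment to finish in July 2023 and version 10.0 is dated 24 October 2023, so a new pre-randomization survey may reach few or no participants in this pilot.

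**Conclusion.** The point holds as a limit on interpretation and precision. As described, the selection score is also the baseline, and it may be about 6 months old at the first group. Within-arm change then includes an expected average fall of 2.6-6.5 points (10-24%) under the assumed distribution. This is an expectation for the group, not a certainty for each adolescent, and its size cannot be fixed from the documents. The 17% (variance) and 9% (standard error) figures rest on three chosen correlations and show the order of the possible gain. Between-arm effects and the primary fidelity and enrollment endpoints are not biased. This is a cheap improvement to secondary analyses, useful because the pilot exists to shape the efficacy trial.

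**What to change.** - Keep the phone CES-D for eligibility only.
- Repeat the CES-D in REDCap at screening visit 2 or at the existing pre-randomization confirmation contact, and do not exclude on the repeat. Add it to Section 6.2.4 and correct Table 7.
- In Section 8.6.2, define the repeat as baseline for change, covariate and moderation, and report the share still above 20.
- In Section 6.2.4, state when the 6-month clock starts and that re-screening repeats the CES-D.
- For adolescents already randomized, label the phone score a screening value and do not read within-arm change from it as intervention effect.
- Carry the repeat CES-D into the efficacy-trial protocol.

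The cost is a few minutes of participant time at a contact that already takes place, a few lines of text, and a less favourable within-arm change. Where enrollment is complete, only the labelling and the future protocol remain to be changed.
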